5.1 Overall Design

This is a Phase 1, single-ascending dose (SAD, Part A) and multiple-ascending dose (MAD, Part B) study of LY3526318 in healthy participants. Both parts are randomized, double-blind, and placebo-controlled.

Part A (SAD):

The single-ascending doses of LY3526318 or placebo will be administered, at planned dose levels of 10, 50, 100, 400, 800, and 1000 mg, in 7 cohorts of 8 participants each, except the expanded 100-mg cohort that will include 12 participants (8 female and 4 male) to accommodate a food effect assessment in the female participants only.

Following a screening period of up to 28 days, eligible participants will be confined to the clinical research unit (CRU) from Day -1 until all study assessments are completed on Day 3. A sentinel dosing strategy will be implemented for the first dose level (Cohort 1, 10 mg). Two participants will receive a sentinel dose (1 each with LY3526318 and placebo) and the remaining participants will be administered LY3526318 after review of safety data up to 48 hours postdose. Participants in Cohort 1 will not be stratified by sex, given that sentinel dosing coupled with stratification by sex may compromise blinding. A fixed number of females and males will be randomized in Cohorts 2 and 3 and the participants will be stratified to ensure equal distribution between females and males. The Part A stratification by sex scheme is shown in [Table 5-1](#).

Table 5-1 **Part A Stratification Based on Sex**

Cohort (Planned dose level ^a)	Number of Females Randomized	Number of Males Randomized	Total Participants Randomized
Cohort 1 (10 mg)	Up to 8 ^b	Up to 8 ^b	8
Cohort 2 (50 mg)	4	4	8
Cohort 3 (100 mg)	8 ^c	4	12
Cohort 4 (400 mg)	8 ^c	NA	8
Cohort 5 (800 mg)	8	NA	8
Cohort 6 (1000 mg)	8	NA	8
Cohort 10 (100 mg)	8 ^d	NA	8

Abbreviation: NA = not applicable.

- ^a Doses may be adjusted based on data obtained in previous study cohorts.
- ^b Cohort 1 will not have a defined stratification by sex scheme. Eight participants will be randomized including males and/or females.
- ^c Female participants in Cohorts 3 and 4 will receive study drug in fasted and fed conditions, separated by a washout period of at least 1 week.
- ^d All 8 female participants in Cohort 10 will receive LY3526318 in a 3-period crossover with standardized high fat meals administered prior to dose, and at 30 min and 1 hour post dose. Participants receiving meals post dose administration will receive their dose in the fasted state. Periods are separated by a washout period of at least 1 week.

Cohorts administered above LY3526318 100 mg are anticipated to exceed the approximate 10x margin to the projected no-observed-adverse-event-level (NOAEL)-equivalent exposure for males; for this reason, only female participants will be enrolled at dose levels higher than 100 mg. Additionally, if exposure data from previous cohorts does not support dose escalation in males through 100 mg, males will be discontinued from further dosing in the study.

The effect of food on LY3526318 PK will be explored in female participants only, in the 100-mg cohort and in the 400-mg cohort. In the 100-mg cohort, the initial dose will be administered after an approximately 8-hour fast in 8 female and 4 male participants, followed by a washout period of at least 1 week. A second dose will be administered after a standardized high-fat meal in female participants only. In the 400-mg cohort, the initial dose will be administered after an approximately 8-hour fast; following a washout period of at least 1 week, the second dose will be administered after a standardized high-fat meal. Except for the food effect assessment cohorts, all other doses are to be administered after an approximately 8-hour fast. Following a review of the 100-mg and/or 400-mg fed and fasted data, subsequent cohorts may be administered with food.

An additional cohort (Cohort 10) will assess the effect of food on LY3526318 PK in 8 female participants. All participants in this cohort will receive 100 mg LY3526318 with standardized high fat meal in an open-label, 3-way crossover manner (meal administered prior to dose, at 30 minutes and at 1 hour post dose; [Table 2-2](#)). Participants receiving meals post dose administration will receive their dose after an approximately 8-hour fast. Periods will be separated by a washout period of at least 1 week.

All participants will return to the CRU for a final visit approximately 9 days after study drug administration or after the fed-state dose for female participants in 100- and 400-mg cohorts.

Part B (MAD):

The multiple-ascending doses of LY3526318 or placebo will be administered, at planned dose levels of 100, 400, and 1000 mg, once daily for 14 days in 3 cohorts of 8 female participants each.

Following a screening period of up to 28 days, eligible participants will receive once-daily treatment with study drug for 14 days. Participants will be confined to the CRU from Day -1 until all study assessments are completed on Day 15 (Cohort 7), Day 18 (Cohort 8) or Day 19

(Cohort 9). Within each cohort, eligible participants will be randomly assigned to receive LY3526318 or placebo in a 6:2 ratio. The first cohort will be administered LY3526318 following a review of safety and PK data through Part A 400-mg cohort and fed period of the 100-mg cohort.

Dose levels will not exceed those administered in Part A. Dose levels in Part B are anticipated to exceed the approximate 10x margin to the projected NOAEL-equivalent exposures for males; for this reason, only female participants will be enrolled in Part B.

[figure not shown]
All doses are planned to be administered in an 8-hour fasting state. However, following a review of the food effect data from Part A, all doses may be administered with food.

Participants will return to the CRU for a final visit on approximately Day 23.

Safety, PK, and other assessments will be performed at time points prescribed in Section 2.

Study governance considerations are described in detail in Appendix 3.

Figure 5.1 illustrates the study design.

Abbreviations: SAD = single-ascending dose (Orange); MAD = multiple-ascending dose (Green).

Note: Doses may be adjusted based on data obtained in previous study cohorts and parts. The timeline listed is an approximation intended to illustrate relative cohort timing within and between Parts A and B. Additional cohorts may be added.

Figure 5.1

Illustration of study design for Protocol J2D-MC-CVAA.

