5.4 Scientific Rationale for Study Design

LY3526318 is a small-molecule TRPA1 inhibitor proposed for FIH dosing in a low uncertainty target and will use a clinical study design with a single cohort (Cohort 1) sentinel dosing strategy. Two oral TRPA1 inhibitors have been administered in healthy participants after being developed by other sponsors (GRC 17536 and ODM-108). Available data show that ODM-108 was well tolerated in healthy participants ([NCT02432664](#)) and GRC 17536 was well tolerated both in healthy participants and in patients with chronic pain conditions ([EU Clinical Trial Register 2012-002320-33](#)). Nonclinical pharmacology studies have demonstrated target engagement through changes in dermal blood flow for TRPA1 activation and antagonism ([Aubdool et al. 2016](#)). Cinnamaldehyde-induced dermal blood flow as measured through laser Doppler imaging (LDI) has been demonstrated to be a translationally relevant biomarker for TRPA1 activation and target engagement ([Buntinx et al. 2017](#)). Serious adverse events in this 14-day study are not anticipated based on the 28-day multiple-dose nonclinical toxicology studies.

This study will include a pilot assessment of food effect in female participants only. In the food effect cohorts, the doses will be administered in fed and fasted states, as indicated. Residual exposure will be minimized with a washout period of at least 1 week between doses. The 100- and 400-mg doses and the high-fat meal were chosen because preclinical data suggest that study drug administration with a high-fat meal may increase exposures of LY3526318 by approximately 5-fold, compared to administration in the fasted state. Having a food assessment at 2 different dose levels will help inform the mode of study drug administration in the MAD and subsequent studies. In addition, because LY3526318 preclinical PK was subproportional to dose, and the effect of food may also be nonlinear, assessing the food effect at 2 different dose levels will provide a better understanding of LY3526318 PK.

CCI

The current study requires safety and PK data for dose escalation. However, the first dose escalation will rely on safety data only because the 10 mg dose is anticipated to result in exposures that have no clinical effect based on preclinical efficacy models that use direct TRPA1 agonists. In addition, 10 mg is anticipated to produce exposures >100x below the NOAEL in males and >1000x below the NOAEL in females.

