7.4.1.1 Part A

Dose escalation from the 10-mg cohort to the 50-mg cohort may occur after review of safety data from at least 6 participants in the 10-mg cohort. The subsequent dose escalations may occur after review of safety and available PK data through 48 hours postdose from at least 6 participants in the prior cohort. The second dose of the 100-mg cohort, food effect assessment, may occur after review of safety and available PK data from the first 3 days of fasted dose in at least 6 participants in Cohort 4 (400-mg dose). The second dose of the 400-mg cohort, in the fed state, may occur after review of Cohort 6 (1000-mg dose) safety and available PK data for at least 6 participants through 48 hours postdose.

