7.4.1.2 Part B

Part A safety and PK data will be reviewed to support initiation of Part B. Based on a review of these data, it will also be decided if the study drug should be administered in the fasted or fed state, and if adjustments to higher dose levels and/or sample collection times in the Part B are deemed necessary.

Dose escalation to Cohort 8 may occur after review of safety and available PK data through 15 days from at least 6 participants of Cohort 7.

Dose escalation to Cohort 9 may occur after review of safety and available PK data through 15 days from at least 6 participants of Cohort 8.

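### If Part B is switched to fed dosing, 14 daily fed 400-mg doses could start before the planned single fed 400-mg dose has been given or reviewed

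*Protocol*

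**What the plan says.** **Fed or fasted.** Protocol 5.1 plans all Part B doses fasted, then allows a switch: "following a review of the food effect data from Part A, all doses may be administered with food". Section 7.4.1.2 places that decision at the review that opens Part B, when "it will also be decided if the study drug should be administered in the fasted or fed state".

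**Start of Part B.** The first cohort is dosed "following a review of safety and PK data through Part A 400-mg cohort and fed period of the 100-mg cohort" (5.1).

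**Escalation within Part B (7.4.1.2).** "Dose escalation to Cohort 8 may occur after review of safety and available PK data through 15 days from at least 6 participants", the participants being those of Cohort 7. In the same form, "Dose escalation to Cohort 9 may occur after review of safety and available PK data through 15 days from at least 6 participants", here of Cohort 8. The fixed ceiling is in milligrams: "Dose levels will not exceed those administered in Part A" (5.1).

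**The fed 400-mg single dose.** Section 7.4.1.1 holds Cohort 4, Period 2 until Cohort 6 (fasted 1000 mg) has been reviewed for at least 6 participants through 48 hours.

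**Stated purpose.** Section 5.4 says: "Having a food assessment at 2 different dose levels will help inform the mode of study drug administration in the MAD". It gives as a further reason that the food effect may not be linear in dose.

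**The concern.** In Part A the protocol does not treat a fed dose as equal to the same dose fasted. Fed 100 mg waits for fasted 400 mg, and fed 400 mg waits for fasted 1000 mg. The Part B gates do not carry this over. If Part B is switched to fed dosing, the written conditions for Cohort 8 can be met with fed data at 100 mg only.

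The first human exposure to fed 400 mg could then be a 14-day daily course, with no single dose and washout before it. If the food effect changes with dose, as 5.4 allows, fed 100-mg data may not predict fed 400 mg. At stake is a review step that the protocol plans for a single dose but does not require before repeated dosing.

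**Working it through.** **1. The gates side by side**

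| Step | Data required by the text | Fed 400-mg single dose required? |
|---|---|---|
| Start Part B and choose fed or fasted (5.1, 7.4.1.2) | Part A through the 400-mg cohort, plus the fed 100-mg period | Not named |
| Cohort 8, 400 mg daily (7.4.1.2) | Cohort 7, at least 6 participants, 15 days | No |
| Single fed 400 mg, Cohort 4 Period 2 (7.4.1.1) | Cohort 6 (fasted 1000 mg), at least 6 participants, 48 hours | It is that dose |

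Could the 400-mg cohort in the start gate include its fed period? Under 7.4.1.1 that period cannot happen until Cohort 6 is reviewed. The gate would then require the 1000-mg cohort as well, and describing it as running through the 400-mg cohort would be odd. The pair that it does name, fasted 400 mg and fed 100 mg, matches the order in 7.4.1.1 before the 800- and 1000-mg cohorts.

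**2. Size, on the dose-multiple basis of 5.5**

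Inputs from 5.5: food factor f = 3 to 5; margins of 5x (female rat) and 10x (female monkey) for fed 400 mg at f = 5.

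The plan's own figures come first. Fed 100 mg: 100 × 5 = 500 mg, below 1000 mg, as 5.5 says. Fed 400 mg: 400 × 5 = 2000 mg. The stated margins then imply NOAEL-equivalent doses of 2000 × 5 = 10,000 mg (rat) and 2000 × 10 = 20,000 mg (monkey). The NOAEL doses are not in the visible text, so the 5x and 10x are taken as given.

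Margin = NOAEL-equivalent ÷ (dose × f):

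| Fed dose | f | Fasted-equivalent | Rat | Monkey |
|---|---|---|---|---|
| 400 mg | 3 | 1200 mg | 8.3x | 16.7x |
| 400 mg | 5 | 2000 mg | 5.0x | 10.0x |
| 1000 mg | 3 | 3000 mg | 3.3x | 6.7x |
| 1000 mg | 5 | 5000 mg | 2.0x | 4.0x |

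**3. Step up to fed 400 mg from the highest exposure already reviewed**

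- Part A order (fasted 1000 mg reviewed): 1200 ÷ 1000 = 1.2 at f = 3; 2000 ÷ 1000 = 2.0 at f = 5.
- Minimum Part B gates (the larger of fasted 400 mg and fed 100 mg): at f = 3, max(400, 300) = 400 and 1200 ÷ 400 = 3.0; at f = 5, max(400, 500) = 500 and 2000 ÷ 500 = 4.0.

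The second line assumes that Cohorts 5 and 6 have not been reviewed when Cohort 8 starts. The text permits this but does not plan it explicitly.

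**4. Accumulation**

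The figures above ignore it, as 5.5 expects none. The Amendment (b) rationale reports a longer half-life in Part A than predicted, without a value. With R = 1/(1 − 2^(−24/t½)), assumed half-lives of 4, 12 and 24 hours give R = 1.02, 1.33 and 2.0. Each margin would be divided by R.

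**The case against.** **The switch has its own condition.** Fed dosing needs review of the Part A food-effect data, and 5.1 describes that assessment as covering both the 100-mg and 400-mg cohorts. The Synopsis and 7.4.1.2 also refer to Part A safety and PK data without limit. The start gate may therefore be only the minimum for the fasted default. This reading is possible, and Figure 5.1 (relative cohort timing) and the redacted parts of 3.2, 3.3 and 5.4 might support it. None of the visible text makes it a condition, however, and the one specific sentence names fed 100 mg only.

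**Other controls apply.** The 7.4.2 stopping rules are binding. The investigator and sponsor must accept each escalation, a dose-escalation report goes to the ethics committee, and doses may be changed after any review. A fed Cohort 7 would also supply full Day 1 and Day 14 fed profiles, including measured accumulation. Later Part A cohorts may themselves be fed, which could close the gap. All of this stands and limits the risk, but none of it requires fed 400-mg single-dose data.

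**The stated margins hold at fed 400 mg.** This is correct if there is no accumulation. The point is the order of review.

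**A stronger reading concerns Cohort 9.** A reader might infer from the table that fed 1000 mg daily breaches a safety limit and that Part B needs an exposure ceiling. The documents do not support that. Section 5.5 calls 5x and 10x acceptable for fed 400 mg and does not set them as minimum margins. They are measured to the highest dose tested, with no findings in females, and subproportional PK would make exposures smaller. Cohort 9 would also follow 14 days of fed 400 mg. A ceiling at the highest Part A exposure would bar doses that meet 5x and 10x. At f = 3 those margins hold up to 2000 ÷ 3 = 667 mg, while the ceiling would be max(1000, 400 × 3) = 1200, and 1200 ÷ 3 = 400 mg.

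**Conclusion.** The gap is in the text as written for the planned doses. If fed dosing is chosen, Cohort 8 can begin 14 days of fed 400 mg without the planned fed 400-mg single dose. This sits badly with 5.4 and with the caution in 7.4.1.1. On dose multiples, the step to fed 400 mg could be 3- to 4-fold where the Part A order would make it 1.2- to 2.0-fold.

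This rests on the 3- to 5-fold food effect in 5.5, dose proportionality, no accumulation, and Cohorts 5 and 6 being fasted and not yet reviewed. The conclusion about the gates needs only the text, with the reservation that Figure 5.1 and the redactions are unseen.

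Section 5.5 justifies fed 100 mg and fed 400 mg only. The lower multiples at fed 1000 mg are context, not a predicted harm.

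Nor should a reader infer that participants were exposed in this way. SAP 6.2 gives 300 mg as the highest Part A dose, a Cohort 3 fed dose cut to 30 mg, a Cohort 4 fed dose of 200 mg, and Part B at 30, 60 and 100 mg. SAP Appendix 4 shows Part B as fasted. This is a modest improvement worth considering.

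**What to change.** Add to Protocol 7.4.1.2:

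> If Part B is given with food, a fed 400-mg cohort may start only after review of safety and available PK data through 48 hours postdose from at least 6 participants in the Cohort 4 fed period.

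The sentence is written for the planned doses; if these change, the dose it names should change with them.

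The cost is a possible delay to a fed Cohort 8, until Cohort 6 and then the Cohort 4 fed period have been reviewed. No participants or procedures are added, because that period is already planned. Fasted Part B is unaffected. An exposure ceiling for fed Part B doses is not recommended.

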5.2 Number of Participants

Part A: Approximately 52 participants will be randomized to achieve 8 evaluable participants per cohort, except the 100-mg cohort that will include 8 evaluable females and 4 evaluable males and 100-mg food assessment cohort (Cohort 10) that will include 8 evaluable females.

The Part A stratification by sex scheme is shown in Table 5-1 and method of treatment assignment is provided in Section 7.2.

Part B: Approximately 24 female participants will be randomized to achieve 8 evaluable participants per cohort (6 LY3526318:2 placebo).

Additional cohorts of up to 8 participants may be enrolled in either part of the study. Such additional cohorts may be enrolled in case intermediate or additional dose level(s) need to be studied or additional food effect need to be studied at other than planned dose levels.

Participants who withdraw from the study before completion of all study activities may be replaced at the discretion of the sponsor.

For purposes of this study, a participant completes the study when all scheduled procedures shown in the Schedule of Activities (Section 2) have been completed.

5.3 End of Study Definition

End of the study is the date of the last visit or last scheduled procedure shown in the Schedule of Activities (Section 2) for the last participant.

5.4 Scientific Rationale for Study Design

LY3526318 is a small-molecule TRPA1 inhibitor proposed for FIH dosing in a low uncertainty target and will use a clinical study design with a single cohort (Cohort 1) sentinel dosing strategy. Two oral TRPA1 inhibitors have been administered in healthy participants after being developed by other sponsors (GRC 17536 and ODM-108). Available data show that ODM-108 was well tolerated in healthy participants ([NCT02432664](#)) and GRC 17536 was well tolerated both in healthy participants and in patients with chronic pain conditions ([EU Clinical Trial Register 2012-002320-33](#)). Nonclinical pharmacology studies have demonstrated target engagement through changes in dermal blood flow for TRPA1 activation and antagonism ([Aubdool et al. 2016](#)). Cinnamaldehyde-induced dermal blood flow as measured through laser Doppler imaging (LDI) has been demonstrated to be a translationally relevant biomarker for TRPA1 activation and target engagement ([Buntinx et al. 2017](#)). Serious adverse events in this 14-day study are not anticipated based on the 28-day multiple-dose nonclinical toxicology studies.

This study will include a pilot assessment of food effect in female participants only. In the food effect cohorts, the doses will be administered in fed and fasted states, as indicated. Residual exposure will be minimized with a washout period of at least 1 week between doses. The 100- and 400-mg doses and the high-fat meal were chosen because preclinical data suggest that study drug administration with a high-fat meal may increase exposures of LY3526318 by approximately 5-fold, compared to administration in the fasted state. Having a food assessment at 2 different dose levels will help inform the mode of study drug administration in the MAD and subsequent studies. In addition, because LY3526318 preclinical PK was subproportional to dose, and the effect of food may also be nonlinear, assessing the food effect at 2 different dose levels will provide a better understanding of LY3526318 PK.

CCI

The current study requires safety and PK data for dose escalation. However, the first dose escalation will rely on safety data only because the 10 mg dose is anticipated to result in exposures that have no clinical effect based on preclinical efficacy models that use direct TRPA1 agonists. In addition, 10 mg is anticipated to produce exposures >100x below the NOAEL in males and >1000x below the NOAEL in females.

According to the International Council for Harmonisation (ICH) guidelines ([ICH 2009](#)), women of child-bearing potential (WOCBP) can be included in early clinical trials without nonclinical developmental toxicity studies (e.g. embryo-fetal studies) in certain circumstances. In this study, participants who are WOCBP will receive 2 weeks of treatment while maintaining adherence to highly effective contraception to mitigate the risk of pregnancy.

5.5 Justification for Dose

The oral dose ranges proposed for this study are 10 mg up to 1000 mg for the SAD, and 100 mg up to 1000 mg once daily for the MAD. Cohorts in the SAD with doses higher than 100 mg and all cohorts in the MAD will only enroll female participants (see justification in Section [5.4](#)). The planned dose levels may be modified (increased or decreased) based on an assessment of safety data and of available PK data during the study.

The proposed dose range of 10 to 1000 mg is supported by preclinical pharmacology studies. In a study in rats, doses of 3 mg/kg or greater (approximately 30 mg in humans) elicited a significant blockade of cinnamaldehyde-evoked dermal blood flow changes as measured through LDI. In addition, doses as low as 0.3 mg/kg (approximately 3 mg in humans) and up to 3 mg/kg showed efficacy in a rat complete Freund adjuvant-induced cold hyperalgesia model; and doses of 3 and 10 mg/kg (approximately 30 and 100 mg in humans) showed efficacy in a rat model of formalin-induced pain behavior. The LDI assay and formalin-induced pain model are expected to be more predictive of target engagement in humans because they use exogenous application of cinnamaldehyde and formalin that are direct agonists of TRPA1 receptor, for which LY is a direct antagonist. Based on these data, the proposed starting dose for this study is 10 mg, which is intended to be lower than the anticipated range of target engagement.

Based on the short elimination half-life ($t_{1/2}$) observed in monkeys after administration of a capsule formulation of LY3526318 hydrate and in a 28-day cynomolgus monkey toxicokinetic study (2 to 4 hours across doses; Study # [00926044](#)), no accumulation is expected upon multiple dosing. Therefore, the margins of safety can be expected to be similar for both single and multiple dose administrations.

Modeling of preclinical data in GastroPlus™ suggests that the bioavailability of LY3526318 may increase by approximately 3- to 5-fold when administered with a high-fat meal, relative to administration in the fasted state. Consequently, the 100-mg cohort (females only) was chosen to explore the effect of food administration, considering that even if a 5-fold increase in exposure is observed, it would not exceed the exposure at the maximum planned dose of 1000 mg. The 400-mg dose was chosen because even if there was a 5-fold increase in exposure, it would provide acceptable margins of safety of 5x and 10x for the NOAEL in female rats and monkeys respectively, based on dose multiples. Of note, there were no findings for either female rats or monkeys in the toxicology studies, hence the NOAEL is the maximum administered dose in those studies.

Thus, the proposed doses for both the SAD and MAD portions of the study are anticipated to be in the target engagement dose range, while providing adequate margins of safety to address the study objectives.

6 Study Population

Eligibility of participants for the study will be based on the investigator's judgment on results of screening medical history, physical examination, vital signs, clinical laboratory tests, and electrocardiogram (ECG). The nature of any conditions present at the time of the physical examination and any pre-existing conditions will be documented.

Screening may occur up to 28 days prior to enrollment.

Prospective approval of protocol deviations to recruitment and enrollment criteria, also known as protocol waivers or exemptions, is not permitted.

